If the true HR is 0.6 under the alternative hypothesis, 196 OS events within each comparison will be required to have 90% power to detect a HR of 0.6 using a one-sided log rank test at a significance level of 0.0115 (overall significance level in the study one-sided 0.025), and a 2-look group sequential design with Lan-DeMets (O'Brien-Fleming) α -spending function to

determine the efficacy boundary and a Gamma Family (-10) β -spending function to determine the non-binding futility boundary

- PFS

It is assumed that the median PFS for patients receiving PLD is 3.5 months,²⁴ and that treatment with avelumab alone or avelumab in combination with PLD is expected to increase the median PFS to 5.8 months, corresponding to a hazard ratio (HR) of 0.6 under the exponential model assumption. The sample size further assumes a 15% drop-out rate within each arm, and non-uniform patient accrual over a 19-month period and minimum follow-up of 12 months after the last patient is randomized.

If the true HR is 0.6 under the alternative hypothesis, 325 PFS events by BICR assessment within each comparison will provide 93% power to detect a HR of 0.6 using a one-sided log rank test at a significance level of 0.001 (overall significance level in the study one-sided 0.025), and a 2-look group sequential design with Lan-DeMets (O'Brien-Fleming) α -spending function to determine the efficacy boundary and a Gamma Family (-10) β -spending function to determine the non-binding futility boundary.

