2. INTRODUCTION

This SAP provides the detailed methodology for summary and statistical analyses of the data collected in study B9991009. This document may modify the plans outlined in the protocol; however, any major modifications of the primary endpoint definition or its analysis will also be reflected in a protocol amendment.

CCI [REDACTED]

Statistical analyses will be performed using cleaned eCRF data as well as non-CRF data (ie, PK concentration, ADA, nAb, CCI [REDACTED]), and tumor assessment results by the Blinded Independent Central Review (BICR)).

The primary analysis will include all data up to a cut-off date which is determined by the number of events for Progression-Free Survival (PFS) by Blinded Independent Central Review (BICR) and for Overall Survival (OS) and minimum follow-up of 12 months after the last patient is randomized. The cut-off date is determined once a data extract (before database lock) is available which indicates that the required number of events for PFS by BICR and for OS and minimum follow-up of 12 months have occurred.

Due to data cleaning activities, the final number of events might deviate from the planned number. The data cut-off date will not be adjusted retrospectively in this case.

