For each of the two PFS comparisons, 325 PFS events by BICR assessment will provide 93% power to detect a HR of 0.6 using a 1-sided log rank test at a significance level of 0.001, and a 2-look group sequential design with Lan-DeMets (O'Brien-Fleming) α -spending function to determine the efficacy boundary and a Gamma Family (-10) β -spending function to determine the non-binding futility boundary.

The analysis cut-off date for the test of the 4 primary hypotheses for OS and PFS will be the same for the IA and, if applicable, for the final analysis. The hypotheses of TTD will be tested at the time of the primary OS and PFS analyses.

The sample size for this study is determined based on the assumptions that the median OS and PFS in control arm is 12 months and 3.5 months, respectively (Gordon et al, 2001; Colombo et al, 2012), and that treatment with avelumab alone or avelumab in combination with PLD is expected to increase the median OS and median PFS to ≥ 20 months and ≥ 5.8 months, respectively, corresponding to a hazard ratio (HR) of ≤ 0.6 under the exponential model assumption. The sample size further assumes a 5% drop-out rate for OS and 15% drop-out rate for PFS within each treatment arm and a non-uniform patient accrual over a 19-month period. The data cut-off for the primary OS and PFS analyses will occur after the target number of events for both endpoints has been reached within each comparison and the last patient randomized in the study has been followed for at least 12 months after randomization.

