5.1.2. Decision rules

OS

To protect the integrity of the study and to preserve the type I error rate, a fraction of alpha (0.002) for OS efficacy will be spent at the interim analysis and accounted for in the overall type I error rate if the interim analysis is performed at the planned number of OS events. The nominal significance levels for the interim and final efficacy analyses of OS will be determined by using the Lan-DeMets procedure with an O'Brien-Fleming stopping boundary. The overall significance level for the efficacy analysis of OS, within each comparison, will be preserved at 0.0115 (1-sided).

Two analyses will be performed for OS:

1. an interim analysis will be conducted after all patients have been randomized in the study and at least 131 (67%) of the 196 OS events for each of the OS comparisons have been documented and
2. the final analysis for OS will be conducted after all patients randomized in the study have been followed for 12 months and at least 196 OS events for each of the OS comparisons have been documented.

PFS based on BICR assessment

All references to PFS in this section pertain to PFS based on BICR assessment even when not specifically stated.

A fraction of alpha (0.0003) for PFS efficacy will be spent at the interim analysis and accounted for in the overall type I error rate if the interim analysis is performed at the planned number of PFS events. The nominal significance levels for the interim and final efficacy analyses of PFS will be determined by using the Lan-DeMets procedure with an O'Brien-Fleming stopping boundary. The overall significance level for the efficacy analysis of PFS, within each comparison, will be preserved at 0.001 (1-sided).

Two analyses will be performed for PFS:

1. an interim analysis will be conducted after all patients have been randomized in the study and at least 267 (82%) of the 325 PFS events for each of the PFS comparisons have been documented based on BICR assessment, and
2. the final analysis for PFS after all patients randomized in the study have been followed for 12 months and at least 325 PFS events for each of the PFS comparisons have been documented based on BICR assessment.

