6.1.2. Progression-free survival as assessed by BICR per RECIST v1.1

6.1.2.1. Primary analysis

The following analyses will be based on the FAS using the strata assigned at randomization. Progression of disease (PD) below refers to PD by BICR assessment.

Progression-Free Survival (PFS) is defined as the time from date of randomization to the date of the first documentation of PD or death due to any cause, whichever occurs first.

PFS data will be censored on the date of the last adequate tumor assessment for patients who do not have an event (PD or death), for patients who start a new anti-cancer therapy prior to an event (see Section 5.2.6) or for patients with an event after 2 or more missing tumor assessments. Patients who do not have an adequate baseline tumor assessment or who do not have an adequate post-baseline tumor assessment will be censored on the date of randomization unless death occurred on or before the time of the second planned tumor assessment (ie, \leq 16 weeks after the date of randomization) in which case the death will be considered an event.

090177e19142bcd4\Approved\Approved On: 09-Jul-2019 05:44 (GMT)

In this study antitumor activity will be assessed through radiological tumor assessments conducted at screening and every 8 weeks until disease progression regardless of initiation of subsequent anti-cancer therapy. The allowable time window for disease assessments is 5 days prior to dosing while on treatment and whenever disease progression is suspected (eg, symptomatic deterioration).

The censoring and event date options to be considered for the PFS and DR analysis are presented in Table 9.

$$\text{PFS (months)} = [\text{date of event or censoring} - \text{date of randomization} + 1] / 30.4375$$

Table 9. Outcome and event dates for PFS and DR analyses

Scenario	Date of event/censoring	Outcome
No adequate baseline assessment	Date of randomization ^a	Censored ^a
PD or death - After at most one missing or inadequate post-baseline tumor assessment, OR - ≤ 16 weeks after the date of randomization	Date of PD or death	Event
PD or death - after 2 or more missing or inadequate post-baseline tumor assessments	Date of last adequate tumor assessment ^b documenting no PD before new anti-cancer therapy is given or missed tumor assessments	Censored
No PD and no death	Date of last adequate tumor assessment ^b documenting no PD before new anti-cancer therapy is given or missed tumor assessments	Censored

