The EDR represents the positive predictive value of investigator assessment and quantifies the frequency with which the investigator declares PFS event earlier than BICR within each treatment arm as a proportion of the total number of investigator assessed events.

The LDR quantifies the frequency with which the investigator declares PFS event later than BICR as a proportion of the total number of discrepancies within the treatment arm.

Discordance metrics are calculated for each treatment arm and, for each metric, the difference in discordance between the experimental and control arms is used to evaluate potential bias. If the discordance is similar across the treatment arms then this suggests the absence of evaluation bias favoring a particular treatment arm. A negative differential discordance for EDR and/or a positive differential discordance for LDR may be indicative of investigator evaluation bias in favor of the experimental arm (Amit et al, 2011).

Exploratory analyses to investigate the impact of potential prognostic or effect modifying (predictive) factors

The same methodology described in Section 6.2.2.1 for OS will be used for PFS based on BICR assessment.

090177e19142bcd4\Approved\Approved On: 09-Jul-2019 05:44 (GMT)

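### Could the final OS test stall because its cut-off waits for 325 BICR PFS events per comparison, with no alternative trigger and no time base for the 15% drop-out?

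*SAP*

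**What the plan says.** SAP 5.1.1 ties the final tests together: "The analysis cut-off date for the test of the 4 primary hypotheses for OS and PFS will be the same" at the interim and, if reached, at the final analysis. The final cut-off "will occur after the target number of events for both endpoints has been reached within each comparison" and the last randomised patient has been followed for 12 months. SAP 5.1.2 repeats the PFS condition: "at least 325 PFS events for each of the PFS comparisons have been documented based on BICR assessment". SAP 2 fixes the date from a data extract "which indicates that the required number of events for PFS by BICR and for OS and minimum follow-up of 12 months have occurred", and accepts departures from the planned count only where data cleaning causes them.

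The sample-size text assumes a "15% drop-out rate for PFS within each treatment arm". Protocol 9.1 says the same: "The sample size further assumes a 15% drop-out rate within each arm". Neither gives the period to which the 15% applies. Both describe 19 months of non-uniform accrual without giving its shape.

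Under SAP 6.1.2.1, PFS is censored "for patients who start a new anti-cancer therapy prior to an event", for an event after two or more missing assessments, and where baseline or post-baseline scans are inadequate. SAP 6.2.2.2 compares investigator and BICR calls; its early discrepancy rate "quantifies the frequency with which the investigator declares PFS event earlier than BICR".

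SAP 5.1.2 and 7.2.1 recompute the final critical value if the number of events differs from the target.

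**The concern.** Needing 325 events from about 367 patients leaves little slack. Treatment stops on investigator progression, but the endpoint needs BICR progression. A patient who progresses by investigator only and then starts new therapy is censored and can never supply an event. The SAP does not say whether the 15% covers such patients.

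If one comparison stalled below 325, the text has no rule for ending the wait. The boundary recalculation applies only once a cut-off exists. The sponsor would then have to delay a final OS test powered on 196 deaths, or choose a cut-off date ad hoc in an open-label trial.

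**Working it through.** **Inputs.** 550 patients 1:1:1, so 2/3 × 550 = 366.7 per comparison and 183.3 per arm. Control medians are 3.5 months (PFS) and 12 months (OS), with HR 0.6 and exponential times. Drop-out is 15% (PFS) and 5% (OS). Accrual takes 19 months and follow-up is at least 12 (SAP 5.1.1). Tables 6 and 7 give the event times (SAP 5.1.2).

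**Power.** For a fixed-sample log-rank test, √325 × |ln 0.6|/2 − 3.090 = 4.605 − 3.090 = 1.514, and Φ(1.514) = 93.5%. With the two-look spending boundary (interim at 267 events, z = 3.447) power is 93.3%. The plan states 93% and Table 7 gives 0.9302, so the figure is reproduced.

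**Timing.** Expected events by month T, summed over arms, are 183.3 × λ/(λ+η) × [1 − exp(−(λ+η)(T−a))], averaged over entry times a. The accrual shape is an assumption, chosen so that the OS times match Table 6: it gives 21.4/27.2 months (HR 1) and 23.5/30.9 (HR 0.6) for 131/196 deaths, against 21.5/27 and 23.5/31 stated. Reading the 15% as loss over 31 months then gives:

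| | Table 7 | Computed |
|---|---|---|
| 267 events, HR 0.6 | 23.5 | 23.4 |
| 325 events, HR 0.6 | 31 | 30.8 |
| 267 events, HR 1 | 21.5 | 21.5 |
| 325 events, HR 1 | 27 | 26.5 |

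Two other readings fail. At 15% per year, only about 313 events are expected at month 31, and 325 come at month 36.0. If 15% of patients never yield an event, the maximum is 0.85 × 366.7 = 312, and 325 could not be reached at all.

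**Ceiling with unlimited follow-up.** λ = ln 2/3.5 = 0.1980 and η = −ln 0.85/31 = 0.00524. Then 183.3 × (0.1980/0.2033 + 0.1188/0.1241) = 183.3 × (0.9742 + 0.9577) = 354.2 events. Extra permanent loss that can be absorbed is 1 − 325/354.2 = 8.2%, or about 30 of 366.7 patients. The ceiling does not depend on the accrual shape.

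**Extra permanent loss on top of the 15%** (assumed, since the documents give no rate). The table shows the month of the 325th event:

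| Extra loss | HR 0.6 | HR 1 |
|---|---|---|
| 0% | 30.8 | 26.5 |
| 2% | 32.6 | 27.7 |
| 4% | 35.2 | 29.2 |
| 6% | 39.8 | 31.6 |
| 8% | 56.7 | 36.9 |

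The 12-month rule already holds the cut-off to month 19 + 12 = 31. Delay attributable to PFS is therefore the excess over 31. Under HR 0.6 that is 1.6 months at 2%, 4.2 at 4% and 8.8 at 6%. Under HR 1 it is nil up to 4% and 0.6 month at 6%.

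**Interim.** This look needs 267 PFS events per comparison, 131 deaths per comparison and full enrolment. With 8% extra loss the 267th PFS event moves only from month 23.4 to 25.4 under HR 0.6.

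**The case for a change.** The strongest reply is that the margin exists only with unlimited waiting. At month 31 the expected count is 325.8, so there is almost none spare at the planned time. These are also expected counts, and both comparisons must get there. The censoring routes are in the plan, and a sentence setting a latest cut-off would be cheap: at 6% extra loss, stopping at month 31 would leave about 306 PFS events and 91.4% power instead of 93.3%.

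The missing time base, the missing trigger and the thin margin at month 31 all stand. What does not follow is that the plan goes wrong:

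- The only drop-out reading of the three that fits Table 7 is the one under which target, timing and power agree.
- PFS carries three times the OS drop-out allowance in the same patients. Loss to follow-up and withdrawal affect both endpoints, so the excess plausibly already allows for PFS-specific censoring. The documents do not say so, but adding 2% to 8% more may count it twice.
- The concordance table in SAP 6.2.2.2 lists possible outcomes and implies no frequency of unconfirmed progression. Protocol Amendment 1 also introduced expedited BICR of investigator-assessed progression.
- OS does not depend wholly on the final look. SAP 5.1.2 lets OS superiority be declared at the interim on OS alone, with probability 0.504 under HR 0.6 (Table 6). Protocol 9.6.4 limits early stopping to crossing both boundaries.
- Waiting buys OS information. At 6% extra loss about 248 deaths would be available, with fixed-sample power Φ(√248 × 0.2554 − 2.273) = 96%, against 90% at 196.

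**Conclusion.** No change is needed. The absent time base is a gap that the SAP's own Tables 6 and 7 let an analyst fill. The common event-driven cut-off is a fair trade-off: all four tests share one date, the target is expected at about the earliest date the follow-up rule permits, and type I error is protected whatever count is reached.

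The residual risk is one of timing at the final look only. It arises if permanent BICR censoring exceeds the 15% allowance, and the target becomes unreachable in expectation only beyond about 8.2% (30 patients per comparison). A contingency rule would need a latest date that nothing in the documents determines, for a shortfall the plan does not predict. Protocol section 9 also reports that the final analysis is complete, so a date fixed ahead of unblinding can no longer be added.

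This rests on exponential event and drop-out times, an accrual shape fitted to Table 6, and the 31-month reading of the 15%. Taking 24 to 36 months instead changes the margin only to 27 to 32 patients. No stated figure needs correcting.

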5.1.2. Decision rules

OS

To protect the integrity of the study and to preserve the type I error rate, a fraction of alpha (0.002) for OS efficacy will be spent at the interim analysis and accounted for in the overall type I error rate if the interim analysis is performed at the planned number of OS events. The nominal significance levels for the interim and final efficacy analyses of OS will be determined by using the Lan-DeMets procedure with an O'Brien-Fleming stopping boundary. The overall significance level for the efficacy analysis of OS, within each comparison, will be preserved at 0.0115 (1-sided).

Two analyses will be performed for OS:

1. an interim analysis will be conducted after all patients have been randomized in the study and at least 131 (67%) of the 196 OS events for each of the OS comparisons have been documented and
2. the final analysis for OS will be conducted after all patients randomized in the study have been followed for 12 months and at least 196 OS events for each of the OS comparisons have been documented.

PFS based on BICR assessment

All references to PFS in this section pertain to PFS based on BICR assessment even when not specifically stated.

A fraction of alpha (0.0003) for PFS efficacy will be spent at the interim analysis and accounted for in the overall type I error rate if the interim analysis is performed at the planned number of PFS events. The nominal significance levels for the interim and final efficacy analyses of PFS will be determined by using the Lan-DeMets procedure with an O'Brien-Fleming stopping boundary. The overall significance level for the efficacy analysis of PFS, within each comparison, will be preserved at 0.001 (1-sided).

Two analyses will be performed for PFS:

1. an interim analysis will be conducted after all patients have been randomized in the study and at least 267 (82%) of the 325 PFS events for each of the PFS comparisons have been documented based on BICR assessment, and
2. the final analysis for PFS after all patients randomized in the study have been followed for 12 months and at least 325 PFS events for each of the PFS comparisons have been documented based on BICR assessment.

The interim analyses for OS and PFS will occur at the same time for both treatment comparisons, ie the analysis cut-off date for the test of the 4 hypotheses, H_{01} , H_{02} , H_{03} and H_{04} , will be the same and will be set after all patients have been randomized in the study and the target number of events across all endpoints and treatment comparisons have been reached. If the value of the test statistic for either of the primary endpoints (either OS or PFS) exceeds the associated efficacy boundary for a comparison, then the experimental treatment associated with that comparison (or treatments if this is met for both comparisons) may be declared statistically significantly superior to the control treatment for that endpoint. If the value of the test statistics for both OS and PFS exceed the associated futility boundaries, then the experimental treatment associated with that comparison (or the study if this is met for both comparisons) may be stopped for futility.

Table 5. Interim Analysis - Efficacy and Futility Boundaries

	Efficacy boundary		Futility boundary	
	z value	p -value	z value	p -value
OS Assuming 131 OS events for each comparison at the time of the IA	-2.8791	0.002	-0.2339	0.4075
PFS Assuming 267 PFS events for each comparison at the time of the IA	-3.4474	0.0003	-1.8938	0.0291

Since the observed number of events at the interim analysis for each comparison may not be exactly equal to the planned 131 OS events and 267 PFS events, the efficacy and futility boundaries will be updated based on the actual number of observed events using the pre-specified α -and β -spending functions. Therefore, the observed Z-test statistic at the interim analysis will be compared with the updated efficacy and futility boundaries.

If the study continues to final analysis, the p-value that will be used to declare statistical significance at the final analysis will be based on the actual number of OS and PFS events documented at the cut-off date for the final analysis and the α already spent at the interim analysis. Therefore, if the interim analysis occurs after exactly 131 OS events for each comparison, and the study continues until the final analysis, the observed p-value for the comparison will have to be < 0.011 to declare statistical significance; if the interim analysis

090177e19142bcd4\Approved\Approved On: 09-Jul-2019 05:44 (GMT)

occurs after exactly 267 PFS events for each comparison, and the study continues until the final analysis, the observed p-value for the comparison will have to be < 0.001 to declare statistical significance. If the number of events in the final analysis deviates from the expected number of events, the final analysis criterion will be determined so that the overall significance level across all analyses and comparisons is maintained at 1-sided 0.025.

Based on the stopping boundaries defined above and the timing of interim analysis at 67% information fraction for OS and 82% information fraction for PFS the design has the following operating characteristics.

Table 6 presents the simulated cumulative probabilities to cross the futility or efficacy boundaries within each comparison for OS at the time of the interim and final analyses and Table 7 presents the simulated cumulative probabilities to cross the futility or efficacy thresholds within each comparison for PFS at the time of the interim and final analyses. Within each comparison, crossing of only one boundary (for either OS or PFS) at interim will not trigger early termination for futility but may trigger early declaration of efficacy.

Table 6. Simulated cumulative probabilities to cross the futility or efficacy boundaries at the interim or final OS analysis

Scenario	Look	Number of OS events ^a	Calendar Time (months)	P(Reject H_{0i}) for OS	P(Reject H_{ai}) for OS
H_{0i} is true (HR=1)	Interim	131	21.5	0.0025	0.5959
	Final	196	27	0.0113	0.9887
H_{ai} is true (HR=0.6)	Interim	131	23.5	0.5040	0.0040
	Final	196	31	0.9008	0.0992

Simulations performed in EAST with number of simulations = 10,000 and seed = 1234.

^a For each comparison; $i=1, 2$.

Table 7. Simulated cumulative probabilities to cross the futility or efficacy boundaries at the interim or final PFS analysis

Scenario	Look	Number of PFS events ^a	Calendar Time (months)	P(Reject H_{0i}) for PFS	P(Reject H_{ai}) for PFS
H_{0i} is true (HR=1)	Interim	267 (PFS)	21.5	0.0001	0.9693
	Final	325 (PFS)	27	0.0011	0.9989
H_{ai} is true (HR=0.6)	Interim	267 (PFS)	23.5	0.7609	0.0117
	Final	325 (PFS)	31	0.9302	0.0698

Simulations performed in EAST with number of simulations = 10,000 and seed = 1234.

^a For each comparison; $i=3, 4$.

090177e19142bcd4\Approved\Approved On: 09-Jul-2019 05:44 (GMT)

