7.2. Interim Analyses and Summaries

At each analysis time point, the critical boundaries for the group sequential test will be derived from the predefined spending function(s) as described in Section 5.1. The calculations of boundaries will be performed using EAST.

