7.2.1. Interim analysis for OS and PFS

Let $u_{OS}(t_1)$ and $u_{OS}(t_F)$ denote the upper critical boundaries based on the test statistics Z_{1_OS} and Z_{F_OS} for efficacy at the interim and the final analysis of OS, respectively, and let $l_{OS}(t_1)$ and $l_{OS}(t_F)$ denote the lower critical boundary for futility at the interim and final analysis of OS, respectively. For the final analysis of OS, $l_{OS}(t_F)=u_{OS}(t_F)$.

Let $u_{PFS}(t_1)$ and $u_{PFS}(t_F)$ denote the upper critical boundaries based on the test statistics Z_{1_PFS} and Z_{F_PFS} for efficacy at the interim and the final analysis of PFS, respectively, and let $l_{PFS}(t_1)$ and $l_{PFS}(t_F)$ denote the lower critical boundary for futility at the interim and final analysis of PFS, respectively. For the final analysis of PFS, $l_{PFS}(t_F)=u_{PFS}(t_F)$.

The critical values $u_{OS}(t_1)$ and $l_{OS}(t_1)$ for the interim analysis of OS are determined such as

$$P_0(Z_{1_OS} \geq u_{OS}(t_1)) = \alpha(t_1^{OS}) \quad \text{and} \quad P_a(Z_{1_OS} \leq l_{OS}(t_1)) = \beta(t_1^{OS}),$$

and critical values $u_{PFS}(t_1)$ and $l_{PFS}(t_1)$ for the interim analysis of PFS are determined such as

$$P_0(Z_{1_PFS} \geq u_{PFS}(t_1)) = \alpha(t_1^{PFS}) \quad \text{and} \quad P_a(Z_{1_PFS} \leq l_{PFS}(t_1)) = \beta(t_1^{PFS}),$$

where P_0 and P_a denote the probabilities under the null hypothesis and the alternative hypothesis, respectively, and $\alpha(t_1^{OS})$, $\beta(t_1^{OS})$ and $\alpha(t_1^{PFS})$, $\beta(t_1^{PFS})$ denote the α and β spent for interim analysis of OS and PFS, respectively, based on the predefined spending functions at information fraction t_1^{OS} and t_1^{PFS} , respectively. (t_1^{OS} is calculated as the ratio of the number of OS events observed at the time of the cut-off for the interim analysis and the total number of OS events targeted for the final analysis; t_1^{PFS} is calculated as the ratio of the number of PFS events observed at the time of the cut-off for the interim analysis and the total number of PFS events targeted for the final analysis).

The boundary for the final efficacy analysis of OS will be calculated such that

$$\alpha(t_1^{OS}) + P_0(Z_{1_OS} < u_{OS}(t_1), Z_{F_OS} \geq u_{OS}(t_F)) = 0.0115$$

The boundary for the final efficacy analysis of PFS will be calculated such that

$$\alpha(t_1^{PFS}) + P_0(Z_{1_PFS} < u_{PFS}(t_1), Z_{F_PFS} \geq u_{PFS}(t_F)) = 0.001$$

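### The final p-value thresholds printed in SAP 5.1.2 (0.011 for OS, 0.001 for PFS) are rounded up from the spending-function results and spend more than the allocated alpha

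*SAP*

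**What the plan says.** SAP Section 5.1.1 allocates one-sided alpha of 0.0115 to each of the two OS comparisons and 0.001 to each of the two PFS comparisons, 0.025 in total. Section 5.1.2 says these levels are preserved within each comparison across a two-look Lan-DeMets O'Brien-Fleming design. Part of each is used at the interim: 0.002 for OS, and for PFS "A fraction of alpha (0.0003) for PFS efficacy will be spent at the interim analysis". Table 5 gives the interim efficacy boundaries as z = -2.8791 (p = 0.002) for OS and z = -3.4474 (p = 0.0003) for PFS.

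For the final analysis, Section 5.1.2 says the p-value needed for significance "will be based on the actual number of OS and PFS events documented at the cut-off date for the final analysis" and on the alpha already used. It then works this out for an interim at exactly the planned counts. With 131 OS events, "the observed p-value for the comparison will have to be < 0.011 to declare statistical significance"; with 267 PFS events, "the observed p-value for the comparison will have to be < 0.001 to declare statistical significance". No z-value is given for either final threshold.

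Section 7.2.1 defines the final boundary by equation: interim alpha plus the null probability of crossing only at the final look must equal 0.0115 (OS) or 0.001 (PFS).

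**The concern.** The PFS figure fails on inspection. If a positive amount of a 0.001 allocation has been used at the interim, and the two looks are not perfectly correlated, the final nominal level must be below 0.001. Yet the printed final threshold is the full 0.001, as it would be in a design with no interim look. The OS figure needs calculation, but it errs in the same direction.

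These are confirmatory decision thresholds. At exactly the planned counts, Sections 5.1.2 and 7.2.1 give different cut-offs for the same test. A final OS p-value between 0.01087 and 0.011, or a final PFS p-value between 0.00091 and 0.001, would be significant under one section and not under the other.

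**Working it through.** **Inputs**
- Alpha per comparison, one-sided: 0.0115 (OS), 0.001 (PFS); SAP 5.1.1.
- Events, interim/final: 131/196 (OS), 267/325 (PFS); SAP 5.1.2.
- Lan-DeMets O'Brien-Fleming α-spending and non-binding futility; SAP 5.1.1. Futility is therefore ignored in the type I error calculation.
- 1:1 allocation within each comparison and HR 0.6 under the alternative; SAP 5.1.1.

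**Step 1: reproduce Table 5.** The spending function is α(t) = 2[1 − Φ(z_{α/2}/√t)], and the interim boundary u₁ satisfies 1 − Φ(u₁) = α(t).

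- OS: t = 131/196 = 0.6684, √t = 0.8175, z_{0.00575} = 2.5271. Then 2.5271/0.8175 = 3.091, α(t) = 0.001994 and u₁ = 2.8791.
- PFS: t = 267/325 = 0.8215, √t = 0.9064, z_{0.0005} = 3.2905. Then 3.2905/0.9064 = 3.630, α(t) = 0.000283 and u₁ = 3.4474.

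Both match Table 5 to four decimals, so this is the SAP's own design. The alternative form 4[1 − Φ(z_{α/4}/√t)] gives 0.00146 and 0.00025 and does not match.

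**Step 2: solve the Section 7.2.1 equation.** Find u_F such that α(t) + P₀(Z₁ < u₁, Z_F ≥ u_F) = α, with corr(Z₁, Z_F) = √t, by numerical integration.

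| | Left for final look | Exact final z | Exact final p | Printed p | z of printed p |
|---|---|---|---|---|---|
| OS | 0.0115 − 0.001994 = 0.009506 | -2.2950 | 0.010867 | 0.011 | -2.2904 |
| PFS | 0.001 − 0.000283 = 0.000717 | -3.1177 | 0.000911 | 0.001 | -3.0902 |

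Using the rounded fractions 0.67 and 0.82 instead gives 0.01086 and 0.00091.

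**Step 3: alpha spent if the printed thresholds are used literally.**
- OS: 0.001994 + 0.009634 = 0.011628, an excess of 0.000128 (0.000128/0.0115 = 1.1%).
- PFS: 0.000283 + 0.000800 = 0.001083, an excess of 0.000083 (0.000083/0.001 = 8.3%).

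**Step 4: effect on the hazard-ratio boundary**, HR = exp(−2z/√d), with z in absolute value.
- OS: exp(−2 × 2.2950/14) = 0.7205 exact; exp(−2 × 2.2904/14) = 0.7209 printed.
- PFS: √325 = 18.028; exp(−2 × 3.1177/18.028) = 0.7076 exact; exp(−2 × 3.0902/18.028) = 0.7098 printed.

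**Step 5: familywise error.** The four per-comparison totals with the printed values sum to 2 × 0.01163 + 2 × 0.00108 = 0.0254. That is only an upper bound, because the tests are positively correlated. The documents give no correlations, so these are assumed: 0.5 between the two comparisons (shared control arm, 1:1:1), and 0 or 0.5 between OS and PFS. In 16 million draws, familywise error with the printed values is 0.0237 (OS-PFS correlation 0) and 0.0233 (0.5). With the exact boundaries it is 0.0233 and 0.0229.

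**Step 6: power with the exact boundaries.** With drift √(d/4) × |ln 0.6|, power is 90.1% for OS and 93.3% for PFS, against the stated 90% and 93%.

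The null rejection rates in SAP Tables 6 and 7 (0.0113 for OS, 0.0011 for PFS) cannot settle the point. With 10,000 runs the Monte Carlo standard errors are about √(0.0113 × 0.9887/10,000) = 0.001 and √(0.0011 × 0.9989/10,000) = 0.0003, both larger than the excesses in Step 3.

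**The case against.** The case for leaving the text alone is substantial. Both figures are correct ordinary roundings to three decimals, so nothing has been miscalculated. They are a conditional illustration, and the sentence that introduces them already says the final level depends on actual events and on alpha already spent. Section 7.2 requires boundaries to be derived from the spending functions in EAST, and Section 7.2.1 fixes the totals at 0.0115 and 0.001. The condition is unlikely to be met: the interim needs at least the target counts in every comparison at a single cut-off, so most comparisons will overshoot, and SAP Section 2 allows that "the final number of events might deviate from the planned number". The overall commitment is 0.025, which the simulated familywise error respects. Table 5 rounds its interim p-values up as well.

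Most of this stands, and it is why the point is minor. It does not remove the inconsistency. Table 5 prints z-values beside its rounded p-values, so no precision is lost there; for the final thresholds the rounded p-value is the only number given. The text does not call the figures approximate. It states what the p-value will have to be. The recalculation clause in Section 5.1.2 is triggered by a deviation in final event numbers, so at exactly the planned counts no sentence says that Section 7.2.1 prevails over the printed value. Section 5.1.2 also promises preservation within each comparison, not only of the 0.025 total, and the printed values break that promise.

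**Conclusion.** The concern holds, at minor severity. The spending rule is sound, but the final thresholds printed from it are rounded in the anti-conservative direction and, at the planned counts, contradict the per-comparison levels that the SAP says are preserved. The excess is 0.00013 per OS comparison and 0.00008 per PFS comparison.

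The threshold and alpha calculations rest on the stated spending function, the planned event counts and non-binding futility, and reproducing Table 5 supports that reading. The familywise figures also rest on the assumed correlations. Protocol Section 9 reports that the final analysis is complete and the primary objectives were not met, so the correction serves the accuracy of the record and any reuse of this text.

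**What to change.** In SAP Section 5.1.2:

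1. Print the final z-boundaries at the planned counts beside the p-values, as Table 5 does for the interim: OS z < -2.2950, PFS z < -3.1177.
2. Round the printed p-values down, to 0.0108 (OS) and 0.0009 (PFS). Used literally, these spend 0.01144 and 0.00099, within the 0.0115 and 0.001 allocated.
3. Add one clause saying that the printed p-values are illustrative and that the boundary computed under Section 7.2.1 from the actual events and the alpha actually spent is the one applied.

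The cost is two z-values, two p-values and one clause. Design, sample size, timing and stated power are unchanged.
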